4.1 Recruitment Plan

Patients will be recruited by referral from outside physicians and from other studies approved by NIH Institutional Review Boards (IRBs).

4.2 Subject Inclusion Criteria

All of the following inclusion criteria must be met prior to enrollment:

1. Molecular diagnosis of the MAGT1 genetic defect
2. ≥6 years years of age

3. Willingness to stop magnesium supplements (other than the study agent) and any multivitamins or over-the counter-supplements that may contain magnesium for the duration of the study
4. Willingness to go without magnesium supplementation during a 12-week placebo period and during both 2-week washout periods (pre-study and mid-study)
5. Willingness to have samples stored for future research
6. Must have a physician at home for follow-up care

4.3 Subject Exclusion Criteria

1. Chemotherapy or radiotherapy for lymphoma within 12 months prior to enrollment
2. Rituximab exposure within 6 months prior to enrollment
3. Systemic symptoms suggestive of evolving lymphoma
4. History of clinically significant cardiac arrhythmias or cardiac defects
5. Renal insufficiency (calculated creatinine clearance <50 mL/min or insufficiency requiring dialysis)
6. Advanced heart block
7. Hypermagnesemia, defined as magnesium serum concentrations >2 mmol/L (>5 mg/dL)
8. Human immunodeficiency virus (HIV) seropositivity
9. Signs or symptoms of life-threatening active microbial infection
10. History of hypersensitivity to any of the study agents
11. Any condition that, in the investigator's opinion, may substantially increase the risk associated with study participation or compromise the study's scientific objectives
12. Participation in a clinical protocol which includes an intervention that, in the opinion of the investigator, may affect the results of the current study

4.4 Justification for Exclusion of Children <6 years old

Ease and maintenance of IV access, lack of a dedicated pediatric intensive care unit, and volume of blood needed for this study will make it very difficult to treat this patient population safely at our center.

5 Study Agent/Interventions

5.1 Disposition and Dispensation

Study agent will be distributed via the NIH Pharmacy according to standard pharmacy procedures.

5.2 Formulation, Packaging and Labeling

Oral magnesium L-threonate capsules will be purchased from commercial sources. The NIH Clinical Center (CC) Investigational Drug Management Research Section (IDMRS) will make a placebo capsule to match magnesium L-threonate. The capsule will consist of a combination of Avicel PH102 and starch 1500 LM to approximately match the weight and density fill of the active ingredient capsule.

The tablets and packaging for magnesium L-threonate and placebo will be identical in appearance. Each bottle will be individually labeled with the patient ID number, dosing instructions, recommended storage conditions, and that the agent should be kept out of reach of children.

No biological test that could potentially unblind the treatment is planned in this study. See Section 13.7 for blinding and unblinding procedures.

5.3 Study Agent Storage and Stability

Magnesium L-threonate should be stored at 15°C to 30°C (59°F to 86°F). MgSO₄ infusions should be stored at 20°C to 25°C (68°F to 77°F). The solution should not be administered unless it is clear and seal is intact. The solution does not contain any preservative. Unused portions should be discarded.

5.4 Preparation, Administration, and Dosage of Study Agent/Intervention(s)

5.4.1 Description

Magnesium L-threonate

Magnesium L-threonate capsules are supplied in size 00 capsules that do not contain markings or engravings. Each capsule contains 48 mg of elemental magnesium for oral administration, cellulose (vegetable capsule), brown rice flour, and may contain one or both of magnesium stearate and silica.

Magnesium sulfate

MgSO₄ injection, USP 50% is a sterile, nonpyrogenic, concentrated solution of MgSO₄ heptahydrate in water for injection. It must be diluted before IV use.

Each mL contains magnesium sulfate heptahydrate 500 mg in water for injection. The pH of a 5% solution is between 5.5 and 7.0. (osmolarity: 4060 mOsmol/L [calc.]; 2.03 mM/ mL MgSO₄ anhydrous; 4.06 mEq/mL MgSO₄ anhydrous).

The solution contains no bacteriostat, antimicrobial agent, or added buffer (except for pH adjustment) and is intended only for use as a single dose injection. When smaller doses are required, the unused portion should be discarded with the entire unit.

5.4.2 Dosing and Administration

Magnesium L-threonate dose escalation

Magnesium L-threonate is an over-the-counter oral magnesium supplement. Each capsule contains 48 mg of elemental magnesium (670 mg magnesium L-threonate), which corresponds to 4 mEq of elemental Mg²⁺. As a dietary supplement, the initial recommended dose is 144 mg of elemental Mg²⁺ taken as 2 capsules (96 mg) in the morning and 1 capsule (48 mg) in the evening. For pediatric and adult patients who are unable to swallow capsules, the capsules may be crushed and mixed with juice or food. Oral magnesium has limited bioavailability and SMCs are tightly regulated via renal excretion. Thus, oral magnesium supplementation at the recommended dose is unlikely to result in levels above 2 mmol/L.

Dose escalation for oral magnesium L-threonate will be based on the patient's weight and tolerance of the supplement. Intolerance is defined as gastrointestinal symptoms (e.g., diarrhea, nausea) after any dose. Patients experiencing intolerance will revert to the last tolerated dose. However, patients with documented renal loss may receive higher doses of magnesium up to 12 tablets a day (48×12 mg/day) as long as serum ionized (free) magnesium remains under 0.59 mmol/L. Patients will escalate their dose of oral magnesium every 2 weeks (**Table 1**).

Patients will be contacted prior to and after each dose escalation to assess tolerance.

In Part I, the maximum tolerated dose for periods A and B will be independent and may differ. For those who participate in Part II, the maximum dose of magnesium will be based on the highest dose tolerated in Part I.

Table 1. Dose escalation of magnesium L-threonate

Patient weight	Starting dose		2 weeks after start		4 weeks after start		6 weeks after start	
	Elemental Mg per day (milligrams)	No. capsules per day	Elemental Mg per day (milligrams)	No. capsules per day	Elemental Mg per day (milligrams)	No. capsules per day	Elemental Mg per day (milligrams)	No. capsules per day
<30 kg	96	2	144	3	192	4	240	5
≥ 30 kg	192	4	288	6	336	7	384	8

No of capsules:	Dosed as:
2	1 morning and 1 evening
3	2 morning and 1 evening
4	2 morning and 2 evening
5	2 morning, 1 afternoon, 2 evening, at ~8 hour intervals
6	2 morning, 2 afternoon, 2 evening, at ~8 hour intervals
7	3 morning, 2 afternoon, 2 evening at ~8 hour intervals
8	3 morning, 2 afternoon, 3 evening, at ~8 hour intervals

Placebo dose escalation

As investigators will be blinded to the treatment group, dose escalation for placebo will also be based on patients' weight and tolerance of the formulation (i.e., absence of gastrointestinal symptoms). The dose escalation schedule for placebo is the same as for oral magnesium (**Table 1**).

Magnesium sulfate

IV MgSO₄ is approved by the Food and Drug Administration (FDA) for the treatment of magnesium deficiency, hyperalimentation, and control of convulsions (seizures). The standard dose of MgSO₄ for the treatment of mild hypomagnesemia in adults is 1,000 mg (8.12 mEq), which is equivalent to 14.3 mg/kg/dose for a 70-kg adult. For pediatric subjects, the starting dose for hypomagnesemia is 25-50 mg/kg/dose. IV magnesium supplementation is often used in the setting of cancer chemotherapy with cisplatin in adults and children [8-10]. IV infusions of MgSO₄ are generally considered safe for use in children with moderate-to-severe acute asthma [6-15]. The National Asthma Education and Prevention Program guidelines suggest 25-

75 mg/kg (maximum 2 grams) of magnesium sulfate for severe asthma exacerbations [11]. The use of magnesium sulfate in the emergency room setting for treatment of children with asthma has been evaluated in several small studies [12-21]. In 5 randomized studies, 182 pediatric subjects with asthma (ages 1 to 18 years) were administered IV infusions of MgSO₄ at single doses of 25-75 mg/kg. Such doses were well tolerated with only minor AEs reported, including epigastric or facial warmth, flushing, pain and numbness at the infusion site, dry mouth, and malaise. Serious adverse effects (eg., hypotension) were not noted in any of the randomized controlled trials of magnesium sulfate in the treatment of asthma in adults or children.

The dose proposed in the current protocol is 30 mg/kg/day administered in 3 daily doses for 3 days. The total daily dose will be 30 mg/kg/day. The rate of IV injection should generally not exceed 150 mg/minute (1.5 mL of a 10% concentration or its equivalent). Solutions for IV infusion must be diluted to a concentration of ≤20% prior to administration, and the rate of administration should be slow and cautious, to avoid producing hypermagnesemia. The diluents commonly used are 5% dextrose injection, USP and 0.9% sodium chloride injection, USP.

This dose was selected based on standard replacement dosing of magnesium sulfate for hypomagnesemia, and to prevent serum concentrations from exceeding 2 mmol/L, the threshold associated with the onset of AEs. Magnesium serum concentrations will be monitored, and the dose will be adjusted not to exceed serum concentrations of 2 mmol/L. We used a similar total dose in a single-subject study of magnesium supplementation in a patient with XMEN and it was very well tolerated.

In the treatment of eclampsia with IV MgSO₄, the recommended initial dose ranges from 4 to 6 g intravenously administered over 15 to 20 minutes. This represents a much higher dose and faster administration rate than proposed in this protocol. The usual plasma concentration achieved in an eclampsia setting is 5 to 7 mEq/L (2.5 to 3.5 mmol/L), but higher levels are not uncommon. Even at these high doses MgSO₄ has been shown to be relatively safe. In a review of 7 trials comparing MgSO₄ to phenytoin for the treatment of eclampsia, MgSO₄ reduced the risk ratios for recurrent seizures, pneumonia and intensive care unit admission and improved perinatal outcomes [22]. Another review comparing MgSO₄ to diazepam reported reduced risks for both seizures and maternal death [23].

Administer with caution if flushing and sweating occurs. Parenteral drug products should be inspected visually for particulate matter and discoloration prior to administration, whenever solution and container permit.

When repeated doses of the drug are given parenterally, serum magnesium levels will be monitored as stated in section 7.2 and subsequent doses will be modified according to **Table 2**. Serum magnesium levels of 3 to 6 mg/100 mL (2.5 to 5 mEq/L) are sufficient to control convulsions. Reflexes may be absent at 10 mEq magnesium/L, where respiratory paralysis is a potential hazard.

Table 2. Dose adjustments according to serum magnesium levels

Serum Mg (>mmol/L)	IV magnesium sulfate	Oral magnesium L-threonate
--------------------	----------------------	----------------------------

≥ 2 - 3.4	Reduce dose by 25%	Dose reduction, at PI's discretion based on patient's current dose
≥ 3.5 – 4.9	Reduce dose by 50%	Dose reduction, at PI's discretion based on patient's current dose
≥ 5	Stop magnesium	Stop magnesium

Dose Adjustments/Modifications/Delays

If gastrointestinal intolerance occurs at grade 2 or higher (NCI CTCAEv4.0 ref), magnesium or placebo will be held until symptoms resolve and then restarted at previously tolerated dose.

Tracking of Dose

During the inpatient portion of the study, magnesium supplementation or placebo will be provided by NIH health care personnel. Research participants will then self-administer oral magnesium L-threonate or placebo according with the dosing scheme in Table 1. Patients will be asked to document any missed doses on the medication log so they can accurately recall the number of missed doses. They will be asked to bring back any remaining study drug at week 12 and 24.

Limitations on Prior Therapy and Use of Ancillary Medications/OTC Products

Magnesium supplements and over-the-counter vitamins or supplements that contain magnesium are not allowed 2 weeks prior to the study start and for the duration of study enrollment.

Subject Access to Study Agent at Study Closure

At the conclusion of the study, participants will have the option to begin a magnesium supplementation regimen under the care of their established primary care provider.

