6.3 Part I: Oral study agent (Week 1 to Week 24)

Oral magnesium or placebo (Week 1 to Week 12)

On Day 0, patients will begin to self-administer the oral study agent according to the dose escalation scheme in section 5.4.2.

Dose escalation every 2 weeks (Weeks 2, 4, and 6, or until maximum tolerated dose is reached)

Prior to increasing the study drug dose the study staff will contact patients to review their medication administration, assess for AEs and approve escalation to the next dose. In addition, patients will be contacted 1 week after dose escalation to assess for AEs.

4-week follow-ups (Weeks 4 and 8 +/- 1 week)

Patients will come to NIH for clinical and research evaluations to include:

- Medical history and physical exam

Clinical laboratory evaluations:

- CBC with differential
- Acute care panel, mineral panel, hepatic panel
- EBV by PCR
- CMV by PCR
- CRP
- ESR
- Total and ionized serum magnesium
- TBNK
- Spot urine magnesium

Research assays:

- Intracellular free Mg²⁺
- EBV FISH
- RNA extraction
- NKG2D expression on CD8 T cells and NK cells by flow cytometry
- Storage of serum, plasma, and PBMCs

Week 12 (+/- 1 week)

At the conclusion of 12 weeks of study agent patients will return to NIH for the following evaluations:

- Medical history and physical exam
- EKG

Clinical laboratory evaluations:

- 24-hour urine collection for magnesium
- CBC with differential
- Acute care, mineral and hepatic panels
- Quantitative immunoglobins
- Lymphocyte phenotyping
- CMV by PCR
- EBV by PCR
- ESR
- CRP
- Total and ionized serum magnesium

Research assays:

- Intracellular free Mg²⁺
- EBV FISH
- RNA extraction
- NKG2D expression on CD8 T cells and NK cells by flow cytometry
- Storage of serum, plasma, and PBMCs

Crossover (Week 13-24 +/- 1 week)

To crossover (from magnesium supplementation to placebo or from placebo to magnesium supplementation), patients will return any unused study agent and begin dose escalation with a new oral agent (magnesium or placebo). Patients will be provided dosing instructions and a medication log for recording AEs (Appendix C).

Dose escalation every 2 weeks (2, 4, and 6 weeks after the start of crossover, or until maximum tolerated dose is reached)

Prior to increasing the study drug dose staff will contact patients to review their medication administration, assess for AEs and approve escalation to the next dose. In addition, patients will be contacted 1 week after dose escalation to assess for AEs.

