8.1 Potential Risks

MgSO₄ IV infusion: The AEs associated with parenterally administered magnesium are usually concentration dependent. Magnesium acts peripherally to cause vasodilation. At low doses, it causes flushing and sweating, while at higher doses, it may cause hypermagnesemia and hypotension, depressed reflexes, flaccid paralysis, hypothermia, circulatory collapse, cardiac and central nervous system depression proceeding to respiratory paralysis. The dose (30 mg/kg/day) selected for the current study is intended to prevent serum concentrations >2 mmol/L, a threshold associated with the onset of AEs. Elevations in Alanine Aminotransferase and Aspartate Aminotransferase have been seen with the administration of IV magnesium.

This product contains aluminum that may be toxic. Aluminum may reach toxic levels with prolonged parenteral administration, if kidney function is impaired. Individuals with renal impairment are not eligible to participate in this study.

Magnesium concentration-dependent toxicity, defined as SMCs >2.1 mmol/L (>5 mg/dL) are associated with decreased deep-tendon reflexes, flushing, and somnolence. Serum magnesium concentrations >4.9 mmol/L (>12 mg/dL) are associated with respiratory paralysis and heart block. Magnesium concentrations will be closely monitored in this study.

Oral magnesium L-threonate: Oral magnesium products are typically well tolerated. The most common AEs are diarrhea and nausea, which are typically dose dependent. Dosing in the current study will be based on weight. If dose-limiting AEs occur, patients will be maintained on the highest tolerated dose. Elevations in Alanine Aminotransferase and Aspartate Aminotransferase have been seen with the administration of oral magnesium.

Phlebotomy: may be associated with discomfort, bruising, local hematoma formation and, on rare occasions, infections, lightheadedness, and fainting. The amount of blood drawn for research purposes will be within the limits allowed for adult or pediatric subjects by the NIH CC (Medical Administrative Policy 95-9: Guidelines for Limits of Blood Drawn for Research Purposes in the Clinical Center).

Venous line placement: Venous catheter insertion is associated with bruising, infection, or clot formation. Using proper placement techniques will minimize these risks.

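### Section 5.2 says no potentially unblinding test is planned, yet serum and urine magnesium are unmasked clinical labs at every on-treatment visit of blinded Part I

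*Combined protocol and SAP*

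**What the plan says.** Section 5.2 states: "No biological test that could potentially unblind the treatment is planned in this study". Section 13.7.1 blinds the participant, the clinical staff and the study team.

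Section 6.3 lists "Total and ionized serum magnesium" among the clinical laboratory evaluations at weeks 4, 8 and 12, separately from the research assays. Urine magnesium is in the same clinical list: "Spot urine magnesium" at weeks 4 and 8, and a 24-hour collection at week 12. Weeks 16 and 20 repeat the week 4 and 8 tests, and week 24 repeats week 12. Appendix B agrees. Section 6.2 adds a 24-hour urine collection and serum magnesium at the post-washout baseline. Section 8.1 says: "Magnesium concentrations will be closely monitored in this study".

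On dosing, section 6.3 provides that before each increase "the study staff will contact patients to review their medication administration, assess for AEs and approve escalation to the next dose". Section 5.4.2 bases escalation on weight and gastrointestinal tolerance, with one exception: patients with documented renal loss may go to 12 capsules a day "as long as serum ionized (free) magnesium remains under 0.59 mmol/L". Table 2 has an oral column in which the PI reduces or stops the dose according to serum magnesium. For placebo, 5.4.2 says: "The dose escalation schedule for placebo is the same as for oral magnesium".

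**The concern.** The plan claims a property that its own schedule does not deliver. The blinded team receives results for the study drug itself, and in a crossover each participant serves as his own comparator: one period against the other, and both against a baseline taken off supplements.

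The people who could infer the period also judge tolerance, approve doses and assign causality. Section 10.1 puts all events on source documents but only reportable ones in CRIMSON, and 10.3 ties documenting and reporting to events thought related to magnesium or study procedures. Section 10.6 halts the study when two or more participants have a similar event of Grade 3 or above thought related to magnesium. Infections, missed school or work days and emergency visits are collected by history (section 7). A guess about the period could influence each of these.

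**Working it through.** **Dose under the exception.** The plan's own product is 48 mg × 12 = 576 mg/day. The Table 1 maxima are 384 mg (30 kg or more) and 240 mg (under 30 kg), so the exception allows 576/384 = 1.5 times or 576/240 = 2.4 times the usual ceiling.

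**Extent of testing.** On-treatment visits are at weeks 4, 8, 12, 16, 20 and 24, which is 6. With 20 planned participants, 6 × 20 = 120 patient-visits carry both a serum and a urine magnesium result.

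**Which results can be compared like with like.**
- 24-hour urine: baseline, week 12, week 24. One value per period, with an off-supplement baseline.
- Spot urine: weeks 4 and 8 against weeks 16 and 20. Two values per period, no spot baseline.
- Serum: baseline and three values per period.

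**Search for masking.** In the text reviewed, no provision withholds magnesium results from the team or routes them elsewhere. The only reader blinding, in 3.1, covers NKG2D and EBV FISH.

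**How informative a result could be.** The plan has no figure for this, and the text reviewed gives neither a within-patient SD nor an expected shift. Part of the background in section 1 was not available, so a figure may exist there. I therefore assume a shift of d within-patient SDs on magnesium, independent normal errors, a constant shift and no carryover. With k like values per period, the difference between period means has SD √(2/k), so

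P(periods ordered correctly) = Φ(d / √(2/k)).

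| d | k = 1 (24-hour urine) | k = 2 (spot urine) |
|---|---|---|
| 0.5 | Φ(0.354) = 64% | Φ(0.5) = 69% |
| 1 | Φ(0.707) = 76% | Φ(1) = 84% |
| 2 | Φ(1.414) = 92% | Φ(2) = 98% |

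At d = 0 both columns are 50%.

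**Timing.** At week 12 only baseline and one 24-hour value are available. The change then has mean d or 0 and SD √2. Cutting at d/2, with either sequence equally likely, a guess is correct with probability Φ(d / (2√2)): 57%, 64% or 76% for d = 0.5, 1 or 2. Between-period comparisons begin only at week 16, and the second 24-hour value arrives at week 24. Escalation decisions fall 2, 4 and 6 weeks into each period, so those of period 1 precede any like-for-like urine comparison.

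**The case against.** The strongest reply is that visible safety labs are a reasonable choice in a trial that enrols children from age 6. Section 5.4.2 notes that "SMCs are tightly regulated via renal excretion", so serum may reveal almost nothing. This stands for serum. It does not help with urine, where excreted magnesium would appear and which is measured at every visit.

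Second, the calculation favours detection. Spot samples at weeks 4 and 16 precede the top dose step, and the crossover has no washout. Both would tend to shrink the contrast. This stands; the table is conditional on its assumptions.

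Third, most period 1 decisions are made before a useful comparison exists, and unblinding follows the week 24 assays. This narrows the exposure to the end of period 1 onward but does not remove it, because the baseline and week 12 24-hour collections can be compared before period 2.

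Fourth, the dosing rules have limited reach. The exception is permissive and restricted to documented renal loss, possibly in no participant. Table 2 is introduced for parenteral dosing, and its lowest threshold of 2 mmol/L is described as unlikely with recommended oral doses. A reader might infer that blinded staff must dose everyone on ionized magnesium; the text does not support that. Nor does the exception's silence on placebo show that it applies only in the magnesium period. With investigators blinded and a common schedule, this reads as a wording gap.

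Fifth, the secondary safety endpoint is incidence and severity, severity is graded by CTCAE, and most events are summarized to the IRB annually (10.4.3). This softens the consequence, but relatedness still governs 10.3 and the halting rule.

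**Conclusion.** The statement in 5.2 is contradicted by 6.3 and Appendix B and should not stand. All participants are exposed to the testing; the renal-loss rule adds to it only for those who use it.

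The degree of unblinding is unknown. The range of 64% to 92% (one value per period) or 69% to 98% (two values) rests on assumed shifts of 0.5 to 2 SDs and falls to 50% if the shift is nil.

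Two stronger readings should be resisted. A reader might average three visits per period for urine and convert the result into a count of participants correctly guessed. Urine is two spot samples and one 24-hour collection, so there is no such average. A reader might also infer that the efficacy result is compromised. The primary endpoints are laboratory measures read by a blinded investigator (3.1), and nothing here alters the comparison, the power or the sample size. What is at risk is judgement-dependent safety recording, the halting trigger and the exploratory history-based outcomes, mainly from the end of period 1.

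**What to change.** 1. Replace the 5.2 sentence with a statement that serum and urine magnesium are measured in Part I and could indicate the treatment, and say how the results are handled.
2. In 13.7.1, send Part I magnesium results to one existing clinician who neither approves doses nor grades adverse events. The medical advisory investigator, already consulted on unblinding in 13.7.2.2, is a candidate. That clinician applies the 0.59 mmol/L limit and Table 2 and relays only continue, hold or step down, with immediate release of values when safety requires it. If the mineral panel reports magnesium, route that value the same way.
3. In 5.4.2, word the renal-loss exception for study agent (magnesium or placebo), in both periods.
4. If the sponsor prefers to keep the results visible for safety, record staff and participant guesses of the period at weeks 12 and 24, before the unblinding in 13.7.2.1, and report them.

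The cost is wording in three sections and result routing for six visits per participant, with no new test. The PI would not see routine magnesium values in Part I, and a relayed hold may be slightly slower. An unexplained step-down could itself be a clue, although gastrointestinal intolerance also causes step-downs. The fallback costs two short questions.

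### Table 2, IV column (Part II only): above the protocol's 2 mmol/L ceiling the dose is reduced but not held, and the 5 mmol/L stop leaves no margin below the stated respiratory-paralysis level

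*Combined protocol and SAP*

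**What the plan says.** Section 5.4.2 sets IV magnesium sulfate at 30 mg/kg/day, given in three infusions a day for three days. One reason for this dose is "to prevent serum concentrations from exceeding 2 mmol/L, the threshold associated with the onset of AEs". The section then commits to a ceiling: "Magnesium serum concentrations will be monitored, and the dose will be adjusted not to exceed serum concentrations of 2 mmol/L". Section 8.1 repeats the aim and describes concentration-dependent toxicity above 2.1 mmol/L. Section 4.3 excludes at entry "Hypermagnesemia, defined as magnesium serum concentrations >2 mmol/L (>5 mg/dL)".

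Section 5.4.2 makes Table 2 the rule for later doses when IV magnesium is repeated. Its IV column reads:

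- 2 to 3.4 mmol/L: "Reduce dose by 25"%
- 3.5 to 4.9 mmol/L: "Reduce dose by 50"%
- 5 mmol/L or more: stop

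On the hazard itself, Section 5.4.2 says: "Reflexes may be absent at 10 mEq magnesium/L, where respiratory paralysis is a potential hazard". Section 8.1 links levels above 4.9 mmol/L with respiratory paralysis and heart block.

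Serum magnesium is scheduled at 24 h, 48 h and completion of the IV course (Section 6.4.2; Appendix B, note g), while infusions run every 8 hours. The IV stopping list in Section 10.7 covers abnormal EKG, advanced heart block, QRS widening, symptomatic hypotension and unexplained syncope. The same section lets the PI pause a subject for any safety issue.

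**The concern.** The text promises adjustment that keeps serum magnesium at or below 2 mmol/L. The table that carries out this promise keeps infusing above that level, at 75% and then 50% of the dose. Its only serum-based stop sits where the protocol itself places respiratory paralysis, so a patient could be at the edge of that hazard with IV magnesium still permitted by the table.

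The stake is the safety of the rare patient, possibly a child, who passes the ceiling during the IV course. Efficacy inference is not at stake, because IV magnesium is given only in open-label Part II.

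**Working it through.** **1. Units, reproducing the plan's figures.** mmol/L = mg/dL × 10 / 24.305, and mmol/L = mEq/L / 2.

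- 12 mg/dL = 4.94 mmol/L (Section 8.1 prints 4.9).
- 5 mg/dL = 2.06 mmol/L (printed as 2 in Section 4.3 and 2.1 in Section 8.1).
- 5 to 7 mEq/L = 2.5 to 3.5 mmol/L, as Section 5.4.2 prints.

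**2. Margin of the stop.** 10 mEq/L = 5.0 mmol/L.

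- Against Section 5.4.2: 5.0 − 5.0 = 0.
- Against Section 8.1: 4.9 − 5.0 = −0.1 mmol/L.

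This step uses only the protocol's own figures and needs no pharmacokinetic assumption.

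**3. Dose still given above the ceiling.** Row 1: 30 × 0.75 = 22.5 mg/kg/day. Row 2: 30 × 0.50 = 15 mg/kg/day.

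**4. Can the planned dose reach these rows?** Section 5.4.1 gives the strength: "Each mL contains magnesium sulfate heptahydrate 500 mg in water for injection", equal to 2.03 mmol. One 10 mg/kg infusion is therefore 10 × 2.03/500 = 0.0406 mmol/kg. As an upper bound, assume no excretion, distribution volume V = 0.2 to 0.5 L/kg and baseline b = 0.7 to 1.0 mmol/L. V and b are not in the documents. The level after n infusions is b + n × 0.0406/V.

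| Time | Infusions given | Level, mmol/L |
|---|---|---|
| 24 h | 3 | 0.94 to 1.61 |
| 48 h | 6 | 1.19 to 2.22 |
| Completion | 9 | 1.43 to 2.83 |

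Rows 2 and 3 are not reached. With V as low as 0.15 L/kg and b = 1.0, nine full doses give 1.0 + 9 × 0.0406/0.15 = 3.44 mmol/L, still below 3.5. A 48 h value of 2 or more needs 0.2436/V + b ≥ 2. Within the assumed ranges that means V no higher than about 0.244 L/kg and b at least 0.78.

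**5. What a hold would change in the worst corner (V = 0.2, b = 1.0).** Assume samples are drawn, and acted on, before the infusion due at that hour.

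- The level passes 2 after the fifth infusion: 1.0 + 5 × 0.203 = 2.015.
- The 48 h sample reads 2.218.
- Under Table 2, three more infusions at 7.5 mg/kg (22.5 mg/kg in all) add 3 × 0.75 × 0.203 = 0.457, ending at 2.675.
- Under a hold, nothing is added and the level stays at or below 2.218.

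**6. Are the cuts large enough? Illustration only.** Suppose instead that the rise above baseline is proportional to dose. After a cut c from level L, the new level is b + (1 − c)(L − b). This is at most 2 only if L ≤ b + (2 − b)/(1 − c).

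- 25% cut: L up to 2.43 (b = 0.7) or 2.33 (b = 1.0).
- 50% cut: L up to 3.3 or 3.0, both below row 2's lower bound of 3.5.
- Cut needed, 1 − (2 − b)/(L − b): 52-58% at 3.4, 54-60% at 3.5 and 69-74% at 4.9.

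This model does not agree with step 4: with no excretion, no cut and no hold lowers the level. It shows direction and is not a measured shortfall.

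**The case against.** The strongest defence is that Table 2 is itself the promised adjustment. It starts to act at 2 mmol/L, and Section 5.4.2 expressly makes it the rule for repeated parenteral doses. That stands. A reader might infer that staff face two competing instructions; the documents do not support this, because the table is plainly operative. What remains is that the table does not do what the text says it is for.

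A reader might also infer that nothing else would stop the drug. That is wrong too. Section 10.7 has the EKG, conduction, hypotension and syncope stops, with EKGs before infusion, at 12, 24 and 48 h, and at completion. It also has the PI-discretion pause and a pause for an SAE or Grade 3+ AE that is unexpected and related. Sections 10.6, 10.7.2 and 10.8 could also act on a laboratory abnormality. These rules give partial protection, but the documents print no serum cut-off for any of them.

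Third, exposure is modest. Each infusion is 10 mg/kg, whereas Section 5.4.2 reports single paediatric doses of 25-75 mg/kg with only minor AEs. Patients with creatinine clearance below 50 mL/min are excluded. Row 1 also largely overlaps levels seen in eclampsia treatment: "The usual plasma concentration achieved in an eclampsia setting is 5 to 7 mEq/L (2.5 to 3.5 mmol/L)", which the section regards as relatively safe. This lowers the severity. It does not create a margin at 5 mmol/L or reconcile row 1 with the stated ceiling.

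Finally, a hold triggered by a sample cannot stop the level passing 2 mmol/L between samples, as the worst corner in the working shows. That is correct: the hold limits further exposure after a high reading, and no more should be claimed for it.

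**Conclusion.** The point holds as a minor, low-probability safety-rule defect confined to the IV course in Part II. The missing margin at 5 mmol/L, and the continued infusion above a ceiling the text says is not to be exceeded, follow from the protocol's own figures.

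A reader might infer that participants are likely to approach paralytic levels. The documents do not support that: at the planned dose the zero-excretion bound ends at 1.4-2.8 mmol/L on the assumed volumes and baselines, and 3.5 mmol/L or more would need a dosing error or loss of renal function. In the worst corner the practical difference is 2.675 against 2.218 mmol/L. A reader might also take the 52-74% cuts as the true shortfall of Table 2; they rest on an assumed rise proportional to dose and are illustrative. The primary analysis is unaffected.

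**What to change.** Change only the IV column of Table 2:

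1. At serum magnesium of 2 mmol/L or more (the existing trigger), hold the next infusion and recheck before each scheduled infusion.
2. Resume at a reduced dose only once the level is below 2 mmol/L.
3. Set permanent IV discontinuation clearly below 4.9 mmol/L, for example at the existing 3.5 mmol/L boundary, a margin of 4.9 − 3.5 = 1.4 mmol/L. The sponsor's clinical team should confirm this value and the restart dose.
4. Add the same serum rule to the IV stopping list in Section 10.7.

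Leave the oral column as it is. As a clerical correction, Section 5.4.2 refers to a Section 7.2 for monitoring, but Section 7 has no numbered subsections; point it to Section 6.4.2.

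Cost: a patient above the ceiling may miss 1 to 3 of 9 infusions (11-33%) after a high 48 h value, or up to 6 of 9 (67%) if already high at 24 h and the level never falls. Each recheck is a 1 mL draw (Appendix B), at most six in all. The Part II comparison of 12 with 24 weeks is within patient after one IV course, so missed infusions bear on both time points and should be recorded. Part I dosing, blinding, sample size and the primary analysis do not change.
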